Primary Objective: This study aims to evaluate the efficacy and safety of high-intensity macro-focused ultrasound in treating facial solar lentigo, as well as its additional effects on the skin using both subjective and objective assessment methods.

III. Study Design:

This study was a prospective, single-center trial, recruited from the First Affiliated Hospital of Nanjing Medical University from November 2023 to February 2024. This trial was approved by the ethics committee (No. 2023-SR-708). All participants have signed written informed consents.

The treatment involves using two ultrasound devices with different focal depths of 3.0 mm (D3.0) and 4.5 mm (D4.5) (MFUS One, Hunan Peninsula Medical Technology Co., Ltd., China) on both sides of the face. After the procedure, an ice pack will be

applied to the treated area for 10 minutes to help reduce redness and swelling. Follow-up visits will be scheduled at 2, 4, 6, and 8 weeks after the treatment. During these visits, clinical images and non-invasive skin assessments will be conducted to monitor your progress.

IV. Study Population

Inclusion Criteria:

- 1.adults between 18 and 70 years old, regardless of gender;
- 2.those who comply the clinical diagnostic criteria for solar lentigo on both sides of the face;
- 3.patients understand and are willing to participate in this clinical trial and voluntarily sign an informed consent form;

Exclusion Criteria:

- 1. Women who are pregnant or breastfeeding, or who plan to become pregnant during the trial period;
- 2.those who are allergic to medical condensation gel;
- 3.those with photosensitive diseases, immune deficiencies, or those who are taking immunosuppressants;
- 4.those with scar physique;
- 5.those with inflammatory or infectious skin diseases;
- 6.those who have systemically used retinoic acid in the last six months or topically applied retinoic acid drugs in the last three months, or have a history of sun exposure in the four weeks prior to treatment;
- 7.those who have undergone high-intensity focused ultrasound treatment within the last six months;

V. Procedures

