Before the treatment, a 2-3mm layer of medical cooling gel will be evenly applied to your face. Two macro-focused handpieces with focal depths at 3.0 mm (D3.0) and 4.5 mm (D4.5) were employed on both cheeks (MFUS One, Hunan Peninsula Medical Technology Co., Ltd., China), targeting both the lesional area and surrounding non-lesional regions while avoiding the periorbital and perioral areas. After the procedure, an ice pack will be applied to the treated area for 10 minutes to help reduce

redness and swelling. Follow-up visits will be scheduled at 2, 4, 6, and 8 weeks after the treatment. During these visits, clinical images and non-invasive skin assessments will be conducted to monitor the improvement. For non-invasive skin assessment, skin elasticity (R-value) and transepidermal water loss (TEWL) were measured using a Cutometer Dual MPA580 (Courage Khazaka Electronic GmbH, Köln, Germany) and Tewameter Hex (Courage Khazaka Electronic GmbH, Köln, Germany), respectively.

VI. Outcome Measures

1. Primary Outcome

Title: Lab* Values of Lesional Area Using Dermoscopy and ImageJ

Description: This outcome measure involves the assessment of lesional areas in dermoscopy images, with the Lab* conversion of pigmentation intensity performed using ImageJ software. L represents the lightness (brightness) of the lesion, where higher L values indicate lighter lesions (improvement). a and b represent the chromatic components (red-green and yellow-blue). Lower values in these components indicate lighter pigmentation, while higher values suggest darker lesions.

Time Frame: week0, week2, week4, week6 and week8

2. Primary Outcome

Title: Physician Global Aesthetic Improvement Scale

Description: The Physician Global Aesthetic Improvement Scale (PGAIS) is a 5-point scale used to rate the global aesthetic improvement in appearance compared to baseline, as judged by the investigator. The scale ranges from -1 (worsening) to 3 (very much improved). The higher score indicates the better improving effect.

Time Frame: week2, week4, week6 and week8

3. Primary Outcome

Title: Subjective Global Aesthetic Improvement Scale

Description: The Subjective Global Aesthetic Improvement Scale (SGAIS) is a 5-point scale used to rate the global aesthetic improvement in appearance compared to baseline, as judged by the patients. The scale ranges from -1 (worsening) to 3 (very much improved). The higher score indicates the better improving effect.

Time Frame: week2, week4, week6 and week8

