4. Primary Outcome

Title: Transepidermal Water Loss (TEWL) Measurement of Lesional Area

Description: This outcome measure involves the assessment of transepidermal water loss (TEWL), which quantifies the amount of water evaporating through the skin. TEWL is a key indicator of skin barrier function and hydration levels. In this study, TEWL was measured using Tewameter Hex (Courage Khazaka Electronic GmbH) that records the rate of water loss through the skin in g/m²/h (grams per square meter per hour). Lower TEWL values (less water loss) suggest an improved skin barrier, which is typically the result of effective treatment and increased skin hydration.

Time Frame: week0, week2, week4, week6 and week8

5. Primary Outcome

Title: Skin Elasticity Measurement of Lesional Area

Description: Skin elasticity was assessed using Cutometer Dual MPA580 (Courage Khazaka Electronic GmbH, Köln, Germany), which measures the skin's resistance to deformation and recovery after deformation. The R-value represents the ratio of skin's ability to resist deformation and its ability to return to its original shape Higher R-values (greater elasticity) suggest that the skin is more resilient and can return to its original shape after deformation, indicating healthy skin with good elasticity and tone.

Time Frame: week0, week2, week4, week6 and week8

IV. Statistical Analysis:

For dermoscopy images, ImageJ software was utilized to perform Lab* conversion on both the lesional and surrounding non-lesional areas. The skin elasticity (R-value), TEWL, skin chroma (Lab* values), and Global Aesthetic Improvement Scale (GAIS) scores were analyzed using repeated-measures analysis of variance (RM-ANOVA) with Greenhouse-Geisser correction to evaluate the statistical significance of treatment effects over time. When interaction effects were observed, simple effects analysis was performed to identify the specific source of the interaction. In cases where no interaction effects were found, the main effects were analyzed. Statistical significance was set at p < 0.05 (two-tailed). All statistical analyses were conducted using SPSS Statistics for Windows (version 26.0; IBM Corp.).

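### RM-ANOVA with no missing-data rule would normally exclude any patient with one missed visit; a mixed model using every attended visit loses less and is less exposed to selective dropout.

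*Combined protocol and SAP*

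**What the plan says.** The final section, Statistical Analysis, analyzes elasticity, TEWL, Lab* and the GAIS scores by "repeated-measures analysis of variance (RM-ANOVA) with Greenhouse-Geisser correction". It names the software ("All statistical analyses were conducted using SPSS Statistics for Windows (version 26.0; IBM Corp") but no procedure or missing-data option.

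Under Procedures, "Follow-up visits will be scheduled at 2, 4, 6, and 8 weeks after the treatment". Under Outcome Measures, Lab*, TEWL and elasticity have five time points ("Time Frame: week0, week2, week4, week6 and week8"). PGAIS and SGAIS have four, with no baseline score ("Time Frame: week2, week4, week6 and week8").

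The design is described in one line: "This study was a prospective, single-center trial". No untreated or randomized comparison group is described. The documents state no sample size, expected dropout, analysis population, imputation method or rule for a missed visit.

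**The concern.** The Greenhouse-Geisser correction belongs to classical RM-ANOVA, which works on one complete row per patient. Without imputation, a patient who misses one visit contributes nothing to that outcome, although the other readings were collected.

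Two things are at stake. The first is precision: collected data are discarded. The second is bias: complete-case results are safe only if missing visits are unrelated to outcome. Patients here see and rate their own faces, so attendance linked to the visible result is plausible. With no comparison group, change over time carries the efficacy claim, and there is no between-group contrast in which such selection could cancel. The non-lesional readings do not help, because they come from the same patients.

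**Working it through.** **Inputs from the plan.** RM-ANOVA for all primary outcomes; four follow-up visits; five time points for Lab*, TEWL and R-value, four for PGAIS and SGAIS. The plan has no figure to reproduce. Missed-visit rates, effect size, within-patient correlation and sample size below are all assumptions.

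**1. Complete rows.** If each follow-up visit is missed independently with probability q, and baseline is always recorded, the share of complete rows is (1 − q)^4. The standard error, relative to full data, grows by 1/√share.

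| q | Complete rows | Follow-up readings collected | Standard error vs full data |
|---|---|---|---|
| 3% | 0.97^4 = 88.5% | 97% | × 1.06 |
| 5% | 0.95^4 = 81.5% | 95% | × 1.11 |
| 10% | 0.90^4 = 65.6% | 90% | × 1.23 |

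**2. How much precision can be recovered.** In simulations with 10% random misses per visit (exchangeable correlation 0.5 or 0.7, n = 40 or 200), the standard error of the week-8 change by maximum likelihood with unstructured covariance, which is what a mixed model fits, was 0.83 to 0.90 of the complete-case value. Multiplying by 1.235 gives 1.025 to 1.11, so about 2.5% to 11% of widening remains.

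**3. Selective dropout that depends on recorded data (MAR).** Assumed: AR(1) correlation 0.7; mean gains of 0, 0.125, 0.25, 0.375 and 0.50 SD at weeks 0 to 8; n = 400. Dropout starts after week 2. A patient whose last recorded change shows no gain leaves at the higher rate, the others at the lower rate.

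| Dropout per visit (no gain / gain) | Patients lost | Complete-case week-8 gain | Error | Maximum likelihood |
|---|---|---|---|---|
| 6% / 3% | 12% | 0.53 SD | +5% | 0.50 SD |
| 8% / 2% | 13% | 0.55 SD | +10% | 0.50 SD |
| 16% / 4% | 24% | 0.61 SD | +22% | 0.50 SD |

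The truth is 0.50 SD; errors are computed before rounding the gains, and simulation error is about 0.005 SD. At n = 30 the 16%/4% case gave 0.60 against 0.49, so the contrast does not depend on a large sample.

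**4. Dropout that depends on the current, unrecorded result (MNAR).** With the same set-up at 16%/4%, complete cases gave about 0.64 SD and maximum likelihood about 0.55 SD. The error falls from 0.14 to 0.05 SD but does not vanish.

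**5. A different set of assumptions.** With exchangeable correlation 0.5 or 0.7, a true gain of 1.0 SD, n = 200 and about 39% of patients incomplete, complete-case error was +19% to +25% under MAR, against about +1% for maximum likelihood. Under MNAR it was +25% to +33%, against +14% to +18%. In the MAR runs the maximum-likelihood standard error was 7% to 9% larger than the complete-case one, so the gain there is in bias, not precision.

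**The case against.** The strongest reply is that the documents do not say incomplete patients are deleted. That is right. A reader might infer a stated deletion rule, but the plan is silent; exclusion follows from the named method as it is normally run. The documented gap is that no missing-data rule exists.

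A reader might also infer that the trial's result is inflated by 22%. The documents do not support that. The follow-up is one treatment and 8 weeks, no dropout figure is given, and 22% is the top of the 5% to 22% range in step 3. With full attendance the effect is zero.

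A third tempting reading is that a mixed model cures both problems. It does not: bias goes only under MAR, and precision returns only in part (steps 2 and 4).

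A fourth is that every primary outcome runs from week 0. PGAIS and SGAIS do not. A patient with no follow-up visit adds nothing to those scores under any model, and early loss cannot be corrected from a baseline score.

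Two further objections stand in part:

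- Patients cannot see TEWL or elasticity readings, so attendance linked to them is less plausible. For those outcomes the case rests more on precision. SGAIS, the patient's own rating, fits the selection mechanism most directly and must not be left out of the remedy.
- The sample may be small. An unstructured covariance over five visits has 5 × 6/2 = 15 parameters. Crossing visit with area for Lab* makes ten readings and 10 × 11/2 = 55 parameters. A fallback and a structured form for Lab* therefore have to be named in advance. Lesions are required on both sides of the face, so the model must also say how the two sides enter.

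**Conclusion.** The concern holds as a choice of analysis that can be improved cheaply. RM-ANOVA with no missing-data rule would, as normally run, drop a patient from an outcome for one missed visit. A mixed model on the same data uses every attended visit and was less biased in every outcome-dependent dropout scenario examined.

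The size is conditional: 88.5% to 65.6% complete rows for 3% to 10% independent misses per visit, and a week-8 gain overstated by about 5% to 22% for MAR dropout from 6%/3% to 16%/4%. These rates are assumed and nothing in the documents confirms or excludes them. The mixed model's advantage is full only under MAR and partial otherwise.

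**What to change.** - **Lab*, TEWL, R-value:** a REML linear mixed model with visit as a categorical factor, all attended visits, unstructured within-patient covariance, and Kenward-Roger or Satterthwaite degrees of freedom. Name the fallback covariance in advance, for example heterogeneous AR(1), then compound symmetry.
- **Lab* only:** add area (lesional or surrounding) and area-by-visit, with a structured rather than fully unstructured covariance across the area-by-visit readings.
- **PGAIS and SGAIS:** a repeated-measures model that likewise uses all attended visits from week 2 to week 8, with a note that patients without any follow-up visit contribute nothing.
- **Two sides of the face:** state whether readings are averaged or modelled separately.
- **Reporting:** the week-8 change with its 95% interval (for PGAIS and SGAIS, the week-8 score, which already rates change from baseline), and the number of patients contributing at each visit.
- **Sensitivity:** keep complete-case RM-ANOVA, and add one delta-adjusted MNAR analysis that makes the unrecorded values worse by stated amounts.

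The cost is plan wording and a different procedure on the same dataset, with slightly more analysis work and no new data. The one downside is possible non-convergence in a small sample, which the named fallback handles.

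### Five outcomes labelled primary (seven variables) are each tested at 0.05 with no multiplicity or success rule; if any one may count, the false-positive risk is well above 5%

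*Combined protocol and SAP*

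**What the plan says.** Section VI of the combined protocol and SAP lists five outcomes, each headed as a primary outcome: Lab* values of the lesion, PGAIS, SGAIS, TEWL and skin elasticity (R-value).

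- Lab* is three measurements. L has its own direction of benefit, and "a and b represent the chromatic components (red-green and yellow-blue", for which lower values count as lighter. Tested separately, these make the total seven variables.
- PGAIS is used to "rate the global aesthetic improvement in appearance compared to baseline, as judged by the investigator". SGAIS is the same rating made by the patient. For both, "Time Frame: week2, week4, week6 and week8", so there is no week-0 value. "The scale ranges from -1 (worsening) to 3 (very much improved" (a five-point scale); the levels in between are not labelled.
- TEWL and elasticity also have a stated direction, for example "Lower TEWL values (less water loss) suggest an improved skin barrier".

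The section headed IV. Statistical Analysis takes the R-value, TEWL, Lab* and GAIS together: "scores were analyzed using repeated-measures analysis of variance (RM-ANOVA) with Greenhouse-Geisser correction". It adds "When interaction effects were observed, simple effects analysis was performed to identify the specific source of the interaction", with main effects analysed if no interaction is found. The only decision criterion is "Statistical significance was set at p < 0.05 (two-tailed". Neither section gives a multiplicity adjustment, a testing order, a lead outcome or visit, an alpha split, or the number of primary outcomes that must succeed.

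**The concern.** The 0.05 level holds for each test. It does not hold for the set of primary outcomes unless the plan says how the results combine, and the plan does not. The Greenhouse-Geisser correction deals with non-sphericity within one ANOVA; it gives no protection across outcomes.

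The labelling makes this worse. Section II separates the treatment of lentigo from other effects on the skin, yet TEWL and elasticity carry the same primary label as lesion colour. As written, a shift in TEWL alone could be presented as a positive primary result of a lentigo trial.

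Lowering the threshold for the planned time tests would not be enough. PGAIS and SGAIS already express change from baseline and start at week 2, so a test over time compares follow-up visits with each other. It can miss a large, steady benefit. Because it has no direction, it can also pass on a decline.

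**Working it through.** **Inputs.** From the documents: alpha 0.05 two-tailed (statistical section), and five outcomes or seven variables (section VI). Not in the documents and therefore assumed: the correlation between outcomes (0 to 0.9, equal for all pairs), the sample size (15 to 40), that one significant variable suffices, and that nothing truly changes. The plan states no familywise error rate, so there is no figure of its own to reproduce.

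**Step 1. Independent tests.** 1 − 0.95^7 = 0.302 and 1 − 0.95^5 = 0.226. For false benefit, at 0.025 per test: 1 − 0.975^7 = 0.162 and 1 − 0.975^5 = 0.119.

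**Step 2. Correlated tests.** For k equicorrelated normal statistics with correlation ρ, the familywise error is

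1 − ∫ [Φ((1.96 − √ρ·x)/√(1−ρ)) − Φ((−1.96 − √ρ·x)/√(1−ρ))]^k φ(x) dx.

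For benefit only, the second Φ term is dropped.

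| Correlation | 0 | 0.5 | 0.8 | 0.9 |
|---|---|---|---|---|
| Seven, either direction | 30.2% | 23.0% | 14.9% | 11.4% |
| Five, either direction | 22.6% | 18.3% | 12.7% | 10.2% |
| Seven, false benefit | 16.2% | 11.5% | 7.4% | 5.7% |
| Five, false benefit | 11.9% | 9.1% | 6.4% | 5.1% |

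One test has 5% in either direction and 2.5% for false benefit.

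**Step 3. The planned time test.** One-way repeated-measures ANOVA with Greenhouse-Geisser correction was simulated with five visits, or four for the two GAIS scales. For the count of five, L stands for Lab*. The runs at n = 20 and 40 used autocorrelation 0.5 between visits (40,000 runs). Those at n = 15 and 30 used independent visits (5,000 runs).

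| n | Seven, correlation 0 / 0.5 / 0.8 | Five, correlation 0 / 0.5 / 0.8 |
|---|---|---|
| 15 | 22.8 / 18.3 / 12.9% | 16.8 / 14.3 / 10.9% |
| 20 | 26.4 / 21.1 / 14.4% | 19.8 / 16.6 / 12.3% |
| 30 | 24.8 / 20.7 / 14.8% | 18.9 / 16.3 / 12.9% |
| 40 | 28.1 / 22.4 / 15.9% | 20.9 / 17.6 / 13.5% |

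The range is about 11% to 28%. It lies below step 2 in places because the correction is conservative in small samples (about 3.6% per test at n = 15).

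**Step 4. Further tests.** The interaction, main-effect and simple-effects tests are not limited in number, so seven is a minimum. As an illustration, two independent tests per variable give 1 − 0.95^14 = 51%.

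**Step 5. The GAIS time test** (n = 20, SD 0.8 and autocorrelation 0.5 assumed, scores rounded and limited to −1 to 3). With a steady true mean of +2 it rejects in 4.3% of runs at 0.05. With scores falling from +0.6 to −0.6 it rejects in 98.5%.

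**Step 6. Effect of Holm.** The first step is 0.05/7 = 0.0071. A test with 80% power at 0.05 has a mean statistic of 1.960 + 0.842 = 2.802. The critical value at 0.0071 is 2.690, so power is Φ(2.802 − 2.690) = 54%.

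**The case against.** The strongest reply is that the percentages depend on a rule that the plan never states. If all primary outcomes had to succeed there would be no inflation. That is correct, but the plan states no such rule, and the missing rule is the defect. Nor does the plan call the study exploratory; it labels outcomes primary and sets a significance level.

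A reader might infer that the trial carries a 30% false-positive risk. The documents do not support that. The 30% belongs to seven independent tests, the least plausible case: L, a and b come from the same dermoscopy images, and PGAIS and SGAIS rate the same appearance. The simulated planned test peaks at about 28%. At correlation 0.9 the normal calculation falls to 10% or 11%, still about twice 5%.

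A reader might also take the false-benefit rates as exact. They come from one-sided normal tests, whereas the planned F test has no direction, so they are approximate. The simulation covers only a time test and not the whole interaction procedure, whose number of tests the documents do not fix.

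Two objections bear on the remedy, and both stand. First, testing the mean GAIS score against zero under Holm does not reliably hold 5%, because the scale has more room above zero than below. With no true change, simulated familywise error was 6.8% (n = 40, SD 1.0), about 11% (n = 40, SD 1.2) and 10.3% (n = 80, SD 1.0). Second, no blinding of the ratings and no control group are described. A constant rating bias of +0.3 (SD 0.8) alone made the mean-score approach positive in 54% of runs at n = 20 and 93% at n = 40. No multiplicity rule cures that.

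**Conclusion.** The point holds. The plan labels five outcomes (seven variables) primary, tests each at 0.05, and does not say what makes the trial positive. That much is certain from the text.

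The size is conditional. If any one significant variable may count, the chance of a false-positive primary result is about 30% to 15% (seven tests) or 23% to 13% (five) at assumed correlations of 0 to 0.8, and about 11% and 10% at 0.9. With the planned Greenhouse-Geisser time test at assumed sample sizes of 15 to 40 and correlations of 0 to 0.8, it is roughly 11% to 28%. False-benefit rates of about 5% to 16%, against 2.5% for one test, are approximate. Interaction and simple-effects tests would add to all of these. The plan should be corrected, and the correction is cheap.

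**What to change.** **Preferred, if no outcome data have been seen.** Name one lesion-colour variable and one visit as primary, test its change from week 0 at 0.05, and make everything else secondary.

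**Otherwise:**

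1. Use one test per variable, on one value per patient, with Holm across the seven (first step 0.0071).
2. For L, a, b, TEWL and the R-value, test change from week 0 to one summary fixed in advance: the mean of the follow-up visits, or week 8.
3. For PGAIS and SGAIS, drop the time test. State the scale's no-change value, then use an exact sign test at week 8 of patients rated improved against patients rated worsened. The lower limit of the scale does not distort this test as it does a mean score.
4. Call a variable positive only if it passes its Holm step in the improving direction given in section VI: higher L, lower a and b, higher PGAIS and SGAIS, lower TEWL, higher R-value.
5. Add a trial-level rule: a claim of effect on lentigo needs at least one of L, a, b, PGAIS or SGAIS to be positive. TEWL and the R-value support only claims about additional skin effects.
6. Report the RM-ANOVA, and any lesional versus non-lesional interaction, as supportive.
7. State that the controlled error concerns no change over time in a study that describes no control group, that the GAIS ratings have no described blinding and remain open to rating bias, and whether outcome data had been seen when the rule was added.

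**Cost.** Revised text in the statistical section and a re-specified primary test for each variable; no new patients, visits or measurements. Power per variable falls: 80% at 0.05 becomes about 54% at the first Holm step (normal approximation). The sign test uses less of the GAIS data and needs at least nine patients rated other than unchanged to pass that step: 2 × 0.5^8 = 0.0078 exceeds 0.0071, while 2 × 0.5^9 = 0.0039 does not.
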